### 5.3 Clinical Study #3: Pharmacokinetics of (-)-Epicatechin in Healthy Volunteers (UCSF)

An open label study in was carried out by [name] at the University of California, San Francisco (UCSF) to assess the safety and pharmacokinetics of a single dose of purified (-)-epicatechin in healthy volunteer subjects (n=9). (-)-Epicatechin doses of 50, 100 or 200 mg were administered in 40 ml of water.

[figure not shown]

### 5.3.1 Safety and Tolerability

No adverse effects were reported or observed in any of the 9 subjects. Subjects specifically denied symptoms of light headedness, dizziness, fatigue, chest discomfort or changes in breathing during the observation period. Data from vital sign monitoring is shown in Figure 30.

At time +0.5 hours there was a trend towards reduced mean systolic blood pressure with a concomitant decrease in heart rate that is consistent with subjects being relaxed, and not with a blood pressure lowering from (-)-epicatechin. In one subject blood pressure at time +0.5 hours decreased markedly, but the value was obtained immediately upon waking, the subject denied symptoms and the heart rate was also reduced from baseline, findings that are consistent with relaxation and not (-)-epicatechin induced vasodilatation.

**Figure 30: Vital signs following (-)-epicatechin administration in healthy subjects.**

### 5.3.2 Pharmacokinetics

Pharmacokinetic parameters for each dose administered are summarized presented in detail in the investigator's brochure. The (-)-epicatechin concentration and metabolite concentration rose rapidly following oral administration consistent with rapid absorption and first pass metabolism as has been previously described [11, 18-21, 45, 47-50]. Complete plasma concentration profiles of (-)-epicatechin and its metabolites after oral administration can be found in the complete PK study report in the investigator's brochure. The shape of the natural log transformed plasma concentration curves was consistent with first order pharmacokinetics.

The ratio of the AUC for (-)-epicatechin and each metabolite to administered dose of (-)-epicatechin is given in Table 6.4. The AUC/dose ratio remains nearly constant for (-)-epicatechin but increases with increasing dose of each of the metabolites suggesting either dose dependent excretion of these metabolites, or perhaps saturation of some competing pathway for epicatechin metabolism. Investigator brochure Table 6.5 shows that  $AUC_{\text{metabolite}}/AUC_{\text{epicatechin}}$  is high for each of the metabolites suggesting that one or more of the metabolites may be an important mediator of biological effects.

### 5.3.3 Conclusions

(-)-Epicatechin was well tolerated over the 50-200 mg dose range, with rapid absorption and first pass metabolism. Non-metabolized (-)-epicatechin represented <5% of the total (-)-epicatechin compounds by 30 minutes. (-)-Epicatechin and its metabolites were rapidly cleared from the body with a plasma elimination half-life of approximately 2.5 hrs for the 100 and 200 mg doses. Plasma concentration of (-)-epicatechin was generally proportional to the administered dose. The 3 dominant groups of metabolites in our study were glucuronidated, sulfated and methyl sulfated, consistent with a recently published evaluation of (-)-epicatechin pharmacokinetics and metabolism [47]. A novel finding in this study was that the  $AUC_{\text{Metabolite}}/AUC_{\text{epicatechin}}$  ratio increased with increasing doses suggesting dose dependency of (-)-epicatechin metabolism.

## 6 RESEARCH DESIGN AND METHODS

### 6.1 Selection and Withdrawal of Participants

#### 6.1.1 Criteria for Enrollment

Ten participants will be studied in this initial pilot project.

##### Participant Inclusion Criteria

- Male
- Age 18 years to 60 years
- Average to low daily physical activity
- Ability to ambulate for 75 meters without assistive devices
- Diagnosis of BMD confirmed by at least one the following:
  - Dystrophin immunofluorescence and/or immunoblot showing partial dystrophin deficiency, and clinical picture consistent with typical BMD, or
  - Gene deletions test positive (missing one or more exons) of the dystrophin gene, where reading frame can be predicted as 'in-frame', and clinical picture consistent with typical BMD, or
  - Complete dystrophin gene sequencing showing an alteration (point mutation, duplication, or other mutation resulting in a stop codon mutation) that can be definitely associated with BMD, with a typical clinical picture of BMD, or
  - Positive family history of BMD confirmed by one of the criteria listed above in a sibling or maternal uncle, and clinical picture typical of BMD.
- Nutritional, herbal and antioxidant supplements taken with the intent of maintaining or improving skeletal muscle strength or functional mobility have been discontinued at least 2 weeks prior to screening (daily multivitamin use is acceptable).
- Hematology profile within normal range
- Baseline laboratory safety chemistry profile within normal range
- No plan to change exercise regimen during study participation

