## 1.3 Study Design

This single center open-label pilot study will enroll 10 adults with genetically-confirmed Becker muscular dystrophy, who will receive the purified nutritional extract (-)-epicatechin 100mg/day orally for 8 weeks. After screening visits, participants will be enrolled in the study if they meet all inclusion criteria. They will be evaluated at baseline and at screening, day 1, and weeks 1, 2, 4 and 8. The main criterion for success of the study will be presence of one or more biologic or strength and performance outcome measures (Aims 1 and 2 below) that yield a response magnitude that allows for sufficient power in a Phase II B study with a sample size of 30 individuals.

Evaluations of efficacy will include:

- Assessment of peripheral blood creatine phosphokinase, follistatin, (-)-epicatechin pharmacokinetics, blood lactate during exercise, and baseline and post-treatment mRNA and miRNA biomarker profiles.
- Assessment of baseline and post-treatment muscle biopsy by histology, Western blot, immunostain and electron microscopy.
- Assessment of strength by isokinetic dynamometry and quantitative grip testing, exercise performance during a standardized recumbent cycle test, muscle perfusion of the quadriceps by NIRS during the exercise test, a 6-minute walk test, and body composition by dual-energy x-ray absorptiometry (DEXA).

Evaluations of safety will include comprehensive review of

- vital signs, height and weight
- medical history
- physical and neurological exam
- previous and concomitant medication history
- electrocardiogram
- laboratory safety panels for hematology and coagulation, standard blood chemistries (lipid, hepatic and metabolic profiles)

This is a greater than minimal risk study with prospect for direct benefit. A medical monitor will review safety-related evaluations throughout the duration of the study.

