*Hypothesis:* Changes in grip strength ( $\geq 5\%$ ), elbow flexion/extension isometric strength ( $\geq 5\%$ ), knee extension isometric muscle strength ( $\geq 1$  pound = 4.448 Newtons), pulmonary function derived maximal static airway pressures (MIP and MEP  $\geq 10$  cm H2O), and regional lean tissue mass by DEXA ( $\geq 2\%$ ) will be clinically significant and correlate with biomarker evidence for muscle regeneration and histological improvement in sarcomere morphology.

*Hypothesis:* Pilot data from exercise performance and strength evaluations in adults with Becker muscular dystrophy will determine the magnitude of response over time that will enable accurate power calculations for future clinical trials.

**Aim 3 (Safety Secondary Endpoints): Evaluation of safety and pharmacokinetic profiles of (-)-epicatechin in adults with Becker muscular dystrophy.** Assessments of safety will include a standard clinical safety panel including hematologic, hepatologic, renal and metabolic profiles. Pharmacokinetic studies will include repeat assessments of trough, 2 hour-post (peak) and 4-hour post dose (-)-epicatechin levels.

*Hypothesis (safety):* (-)-epicatechin given at 100mg/d orally will display an acceptable safety profile in BMD patients.

*Hypothesis (pharmacokinetics):* (-)-epicatechin given at 100mg/d orally in BMD patients will produce pharmacokinetic profiles similar to those seen in previously described studies in the literature.

**Aim 4 (Pilot Biomarker Endpoints): Pilot evaluation of disease- and epicatechin-specific circulating mRNA and miRNA blood profiles as pilot biomarkers for monitoring treatment efficacy.** Epicatechin stimulates follistatin expression in tissue and blood. In addition to its effects on muscle regeneration, follistatin is known to exert anti-inflammatory and anti-fibrotic effects via antagonism of activin and myostatin.

*Hypothesis:* Using gene array assays directed toward fibrosis- and inflammatory-oriented pathways, we expect treatment with (-)-epicatechin to induce detectable pre-/post-treatment differences in mRNA and miRNA expression that may be utilized as biomarkers of treatment effect for future clinical trials.

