## 2 BACKGROUND AND SIGNIFICANCE

### 2.1 Becker Muscular Dystrophy

Muscular dystrophies are a group of diverse genetic diseases featuring progressive muscle weakness, degradation of muscle fibers, and loss of function [23]. BMD is an inherited disease primarily seen in males, with an incidence of 3-6 per 100,000 live births [24]. Onset of symptoms can occur over a wide age range, with most patients diagnosed between 5 and 15 years of age [25]. BMD is characterized by progressive muscle loss (sarcopenia), with loss of strength, muscle injury, degeneration, atrophy, and eventually fibrosis [25]. Most patients can no longer walk by age 25-30, and lung (e.g., breathing problems, infections) and heart (e.g., cardiomyopathy) complications can significantly reduce lifespan [25].

Many muscular dystrophies, including BMD and the more common Duchenne Muscular Dystrophy (DMD), result from mutations in the gene encoding dystrophin, a key subsarcolemmal protein in the dystrophin-associated protein complex (DAPC) at the muscle cell membrane [26, 27]. The DAPC links the muscle cytoskeleton with the extracellular matrix and appears to play a role in muscle stabilization during contraction as well as nNOS signaling [28, 29]. Loss of dystrophin destabilizes the DAPC and results in abnormal muscle membrane permeability, detectable as large elevations in plasma creatine kinase at birth and before the appearance of physical symptoms [30]. BMD is attributed to quantitative or qualitative decrements in dystrophin expression rather than complete or near-complete loss of dystrophin as in DMD.

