### 6.3.2 Criteria for Dose Reductions

Dose reductions will occur due to adverse drug events and participants will not have their doses re-escalated during the course of the study. Criteria for dose reduction will include:

- Peak (-)-epicatechin PK level >4umol/ml
- Recurrent non-manageable headache
- Increase in baseline safety evaluations >1.5 ULN or 100% change from baseline, excepting CK, AST, ALT
- Abnormal coagulation studies (PT/PTT)
- Other Grade 4 adverse event

If participants require a dose reduction based on the criteria listed above follow the guidelines in Table 4 when reducing a participant's study medication dose.

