## **9 ASSESSMENT OF SAFETY**

### **9.1 Safety Parameters**

Safety parameters for this study will include:

- Review of Systems
- Review of Adverse Events

- Laboratory Assessments: Concurrent with peripheral blood draws listed in the efficacy section and according to the study visit procedure chart, participants will provide blood samples for standard clinical safety testing. Safety panels will include:
  - CBC/Diff
  - PT/PTT
  - CPK
  - Total cholesterol
  - Albumin
  - Total Bilirubin
  - Conjugated Bilirubin
  - GGT
  - ALT/AST
  - Alkaline Phosphatase
  - Sodium
  - Potassium
  - CO2
  - Chloride
  - Calcium
  - BUN
  - Serum Creatinine
  - Serum Glucose
  - Serum Total Protein
  - Fasting lipid profile
  - BNP
- EKG
- Review of Medical History
- Review of Medical and Surgical Events
- Physical and Neurological Exam
- Review of Medication History
- Review of Current Medications and Therapies
- Review of any Adverse Events
- Collection of Vital Signs
- Collection of Height & Weight

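### The 6.1.1 entry rule requiring a normal safety chemistry profile lacks the CK, AST and ALT exception that 6.3.2 applies on treatment

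*Combined protocol and SAP*

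**What the plan says.** All references are to the combined protocol and SAP.

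- **Entry rule.** The inclusion list in 6.1.1 contains "Baseline laboratory safety chemistry profile within normal range", with no analyte exempted. Section 1.3 makes the list binding: "participants will be enrolled in the study if they meet all inclusion criteria". Section 6.1.2 has the site confirm this before entry.
- **Panel contents.** Section 9.1 states that "participants will provide blood samples for standard clinical safety testing. Safety panels will include", and the list that follows includes CPK and ALT/AST. Summaries elsewhere are shorter. Section 1.3 names the chemistry part as lipid, hepatic and metabolic. Aim 3 in 1.4 speaks of "a standard clinical safety panel including hematologic, hepatologic, renal and metabolic profiles".
- **Treatment-phase rule.** Section 6.3.2 makes this a reason to reduce the dose: "Increase in baseline safety evaluations >1.5 ULN or 100% change from baseline, excepting CK, AST, ALT".
- **Disease background.** Section 2.1 says that the membrane defect following dystrophin loss is "detectable as large elevations in plasma creatine kinase at birth and before the appearance of physical symptoms". Of Becker disease itself it says: "BMD is characterized by progressive muscle loss (sarcopenia), with loss of strength, muscle injury, degeneration, atrophy, and eventually fibrosis".

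**The concern.** The plan recognises in one place that CK, AST and ALT cannot be read in this population as ordinary safety chemistry, and exempts them. In the place where laboratory values are first used to make a decision, the exemption is absent. A site following the text would have two options for a man whose only abnormality is a raised muscle enzyme: refuse him, or enrol him against a stated criterion.

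Refusal slows recruitment to a study of 10 and tilts the sample towards men with normal enzymes. It would also leave less room for a fall in CPK, which 1.3 and 8.1 list as an efficacy blood test. Enrolment leaves an eligibility deviation on record for each such man, because eligibility is checked against the text and not against what the authors may have meant.

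**Working it through.** The plan gives no figure on this point to reproduce, so the check is mainly a comparison of sections.

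**Step 1. Will the rule be applied to actual values?** Yes. Table 3 schedules safety blood at screening and at baseline, and 1.3 and 6.1.2 require every inclusion criterion to be met.

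**Step 2. Are the three enzymes in the profile, and are they expected to be raised?**

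| | In the chemistry profile? | Raised in this disease? |
|---|---|---|
| AST, ALT | Yes through the hepatic profile in 1.3; itemised in 9.1 | Not stated; implied only by the 6.3.2 exception |
| CK | Itemised in 9.1. The 6.3.2 exception is needed only if CK is otherwise a baseline safety evaluation. Against: 1.3 names CPK under efficacy, and Aim 3 names no muscle enzyme | Section 2.1 ties large elevations to dystrophin loss and describes muscle injury in BMD; 4.1.10 treats excess plasma CK as a recognised sign of muscle damage |

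**Step 3. Does any section extend the exception to entry?** None does. The exception appears only in 6.3.2.

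**Step 4. Size.** The only input from the documents is n = 10 planned participants (6.1.1). Let q be the share of otherwise eligible men with at least one of the three enzymes above range. The documents give no value for q, so every value below is an assumption.

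- If such men are enrolled anyway: expected deviations = 10q, and the chance of at least one = 1 − (1 − q)^10.
- If the rule is enforced: expected number of otherwise eligible men screened to enrol 10 = 10/(1 − q).

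| Assumed q | Expected deviations | Chance of at least one | Men screened if enforced |
|---|---|---|---|
| 0.05 | 0.5 | 1 − 0.95^10 = 0.401 | 10.5 |
| 0.10 | 1.0 | 1 − 0.90^10 = 0.651 | 11.1 |
| 0.25 | 2.5 | 1 − 0.75^10 = 0.944 | 13.3 |
| 0.50 | 5.0 | 1 − 0.50^10 = 0.999 | 20 |
| 0.80 | 8.0 | above 0.999 | 50 |
| 0.95 | 9.5 | above 0.999 | 200 |

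The limits are 0 deviations at q = 0 and 10 at q = 1. With the exception written into the entry rule, deviations from these three enzymes are 0 at every q.

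**The case against.** The best reply is that neither enzyme group has both links stated. CK is the one the background section reports as raised, yet the summaries in 1.3 and 1.4 leave it out of the safety chemistries. AST and ALT sit within the hepatic profile, yet no section says they are raised in BMD. The CK sentence in 2.1 refers to loss of dystrophin and to findings at birth, and 2.1 then distinguishes BMD from complete or near-complete loss. The 6.3.2 exception governs change on treatment, so it could reflect fluctuation after open biopsy and exhaustive exercise and need not mean abnormal entry values.

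This stands as a limit on certainty. It does not remove the gap. The only itemised panel contains all three enzymes, 6.3.2 treats them as needing an exemption, and the entry rule offers none.

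Three stronger readings are tempting and are not supported:

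- **That the list contradicts itself by also requiring typical BMD.** In 6.1.1 that word describes the clinical picture. No section defines it by enzyme levels.
- **That tying the bullet to the 9.1 list would newly subject lipids and glucose to the rule.** Section 1.3 already counts lipid and metabolic profiles among the chemistries, so on the reading that brings in AST and ALT, lipids and probably glucose are covered now.
- **That deviations are more likely than exclusions because of who runs the site.** The documents say there is one centre. They do not say how it would handle the rule.

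**Conclusion.** The point holds as an omission in a binding entry rule, with medium confidence. It rests on two readings: that AST and ALT belong to the profile because 1.3 includes hepatic chemistry, and that CK belongs because 9.1 lists it and 6.3.2 has to except it. It also assumes that some eligible men have raised values, which 2.1 and 6.3.2 make reasonable but do not quantify.

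Its size cannot be fixed from the documents. The range of 0 to 10 men is the whole possible range, and the table of assumed shares shows only how quickly deviations accumulate if raised values are at all common.

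A reader might infer that the rule undermines the primary analysis by selecting men with normal CK. The documents do not support that. CPK is a listed efficacy test, but no hypothesis under Aim 1 or Aim 2 names it, and no effect on the named primary hypotheses is claimed. The consequence is either a narrower sample or avoidable deviations. The plan should be corrected because it states a rule that misfires and already contains the wording that would repair it.

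**What to change.** Amend the 6.1.1 bullet to read: "Baseline laboratory safety chemistry profile within normal range", excepting CK, AST, ALT. This repeats the 6.3.2 exception. Judge liver status at entry by GGT, total and conjugated bilirubin and alkaline phosphatase, all already in 9.1, together with the existing exclusion for significant hepatic impairment.

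The cost is four added words, with no new procedure and no change to the planned 10 participants. The small downside is that AST and ALT no longer screen for liver disease at entry. The amendment does not define the rest of the profile, so deviations arising from other analytes are left as they are.

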##### Participant Exclusion Criteria

- Currently enrolled in another treatment clinical trial.
- History of significant concomitant illness or significant impairment of renal or hepatic function.
- Use of regular daily aspirin or other medication with antiplatelet effects within 3 weeks of first dose of study medication.
- Regular participation in vigorous exercise.
- Symptomatic heart failure with cardiac ejection fraction <25%

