### 6.3.4 Concomitant Therapy

No new medications may be taken, except over the counter cold remedies, daily multivitamin, and Zantac, during the study period without the agreement of the Study Chair. The exception is any case where such medications are used to prevent injury or disability due to unforeseen adverse events.

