## 10.7 Potential Risks

### 10.7.1 Risks of Epicatechin

Animal and human safety studies suggest that (-)-epicatechin at doses of 1-2 mg/kg should be safe and well tolerated. In a study with green tea extracts containing (-)-epicatechin given orally to rats daily for 6 months, the no-observable-adverse-effect level (NOAEL) corresponded to 85 mg (-)-epicatechin/kg [67]. For the human dosing plan of 1 mg/kg, this provides a safety margin relative to the rat NOAEL of at least 85X. The dosing plan is also supported by published human studies, in which (-)-epicatechin doses of 1 and 2 mg/kg were administered with no adverse events were reported [11]. Potential risks based on the biological activities of (-)-epicatechin include:

**Hypotension** Given the reported effects of (-)-epicatechin on blood vessels, it is reasonable to assume that a potential risk may be associated with vasodilation. Of note is the fact that so far, no blood pressure reducing effects by (-)-epicatechin have been reported in normal subjects [81]. With cocoa based studies, blood pressure reducing effects are only reported in humans that have high blood pressure [81]. There is the possibility that patients undergoing pharmacologic treatment for high blood pressure if given (-)-epicatechin may develop hypotension through additive or synergistic effects.

**Migraines** The facilitation of migraines has been associated with the action of vasoactive substances [82]. The consumption of cocoa products has been reported to be associated with increased likelihood of migraine development [83, 84]. Thus, it is reasonable to surmise that (-)-epicatechin may increase the chances for migraine development in susceptible individuals.

**Bleeding** Anti-clotting like effects have been described for multiple members of the flavonoid family including (-)-epicatechin [85]. There is no report as to the effects that (-)-epicatechin per se may have on phenomena such as platelet aggregation or clotting times. There is a limited number of reports on the effects of cocoa on these endpoints. In general, they report effects on platelet aggregate. As with any compound, hypersensitivity reactions may occur, although no such reactions have been seen to date.

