**Contraindications and Warnings** No contraindications are known. However, due to the possibility that (-)-epicatechin may interact with drugs with known antiplatelet effects to potentiate their activity, participants who are currently on long-term therapy with any such agents will be excluded from the study.

**Overdose** Neither the effects of overdose of (-)-epicatechin nor an antidote to overdose are known. The intraperitoneal (-)-epicatechin median lethal dose (LD50) reported for mice is 1000 mg/kg as stated in the MSDS provided by suppliers such as Sigma-Aldrich.

**Pregnancy and Lactation** In a developmental toxicity study in pregnant rats using a green tea extract, the no-observable-adverse-effect level (NOAEL) corresponded to 100 mg (-)-epicatechin/kg (the highest dose tested)[68]. No information is available on levels of (-)-epicatechin in breast milk. Risks of

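### The entry rules bar antiplatelet drugs but not an anticoagulant already in use, and do not clearly require a PT/PTT result, before two planned open biopsies

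*Combined protocol and SAP*

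**What the plan says.** **Drugs.** The Participant Exclusion Criteria in section 6.1.1 list "Use of regular daily aspirin or other medication with antiplatelet effects within 3 weeks of first dose of study medication". Section 10.7.1 (Contraindications and Warnings) gives the reason, "due to the possibility that (-)-epicatechin may interact with drugs with known antiplatelet effects to potentiate their activity", and the consequence: "participants who are currently on long-term therapy with any such agents will be excluded from the study". Section 6.3.4 adds "No new medications may be taken, except over the counter cold remedies, daily multivitamin, and Zantac, during the study period", unless the Study Chair agrees. None of these sections mentions anticoagulants.

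**Bleeding risk.** Under its Bleeding heading, section 10.7.1 says "Anti-clotting like effects have been described for multiple members of the flavonoid family including (-)-epicatechin" and then "There is no report as to the effects that (-)-epicatechin per se may have on phenomena such as platelet aggregation or clotting times".

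**Laboratory entry criteria.** The Participant Inclusion Criteria ask for "Hematology profile within normal range" and for a normal baseline safety chemistry profile. Coagulation is not named. Section 1.3 names hematology and coagulation as two items in the safety panels, and section 9.1 gives PT/PTT its own line apart from the blood count. Table 3 draws safety blood at Screening and on Day 1.

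**Biopsies.** Section 8.1 plans an open biopsy of the biceps at baseline and another after 8 weeks of dosing. Table 3 puts the first on Day 1.

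**The concern.** The protocol identifies bleeding as a possible effect of the study agent and says that nothing is known about its effect on clotting times. It turns that worry into an entry rule for one class of drug only. An anticoagulant is not normally described as a drug with antiplatelet effects, so a site applying section 6.1.1 as written has no rule under which to exclude a man who takes one. Section 6.3.4 does not help, because his drug is not new.

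The laboratory criteria could have served as a second check, but they leave open whether clotting tests count. A site could enrol a man and take the Day 1 biopsy without having treated PT/PTT as an eligibility result.

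The stake is the safety of individual men having open surgery for research purposes. Nothing here touches the success criterion, the endpoints or the sample size.

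**Working it through.** The plan gives no figure on this point, so the check is mainly a comparison of the relevant sections.

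1. **Is an anticoagulant already in use barred by name?** Section 6.1.1: antiplatelet effects only. Section 10.7.1: the words any such agents refer back to antiplatelet drugs. Section 6.3.4: new medications only. Result: no.

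2. **Is it barred by a general rule?** The nearest is "History of significant concomitant illness or significant impairment of renal or hepatic function". It turns on a judgement about the illness and names neither anticoagulants nor bleeding disorders. The only heart-specific exclusion is symptomatic failure with an ejection fraction below 25%, so lesser heart disease is not clearly barred. Result: some such men may be excluded, but not by a stated rule.

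3. **Is PT/PTT an entry condition?** Two readings are open. Aim 3 in section 1.4 sorts the safety panel into hematologic, hepatologic, renal and metabolic profiles, and PT/PTT would fit best under the first. Sections 1.3 and 9.1 separate coagulation from hematology and from the blood count. Section 6.1.2 ties enrolment to verification of the inclusion criteria, which do not name the test. Result: unclear.

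4. **Is the test already done?** Yes. PT/PTT is in the section 9.1 panel, and Table 3 draws safety blood at Screening. The protocol attaches no entry decision to the result.

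5. **How many procedures?** 10 men × 2 biopsies = 20 planned biopsies. One man on an anticoagulant would be 1 of 10 men and 2 of 20 biopsies. This describes the design and is not a rate.

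6. **What might the added criterion cost?** The documents give no screen-failure rate. Assume that a fraction f of otherwise eligible men fail it. Enrolling 10 then needs 10/(1 − f) men, so the extra number screened is 10/(1 − f) − 10:
   - f = 1%: 10/0.99 − 10 = 0.10
   - f = 5%: 10/0.95 − 10 = 0.53
   - f = 10%: 10/0.90 − 10 = 1.11

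   Over this assumed range the cost is about 0.1 to 1.1 extra men screened.

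**The case against.** The strongest reply is that the antiplatelet-only exclusion matches the evidence the protocol cites. The sentence on anti-clotting effects rests on a single reference which, by its title, is about cocoa and platelet function. Section 10.7.1 then says the cocoa reports generally concern platelet aggregation. Clotting times are mentioned only to say that no report exists. This stands. A reader might infer that the protocol contradicts itself by recognising a clotting effect and then ignoring it. The text does not go that far: it records an unknown, and widening the exclusion is a precaution.

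The second reply is that other controls exist. Table 3 has medications reviewed at Screening and Day 1, the significant-illness exclusion gives the investigator discretion, and section 8.1 allows biopsy under the hospital's usual procedures, which may include clotting checks. A site may also read the hematology criterion as including PT/PTT. These points lower the risk. None tells the site what to do about an anticoagulant or a prolonged PT/PTT.

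Two further inferences are tempting.

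- A reader might take the drug break in section 6.3.3 as showing that one is missing before the Week 8 biopsy. That rule covers an unanticipated operation after a serious adverse event and gives no reason for the break, so it does not bear on a planned biopsy.
- A reader might expect the PT/PTT dose-reduction trigger in section 6.3.2 to cut exposure in men whose values were abnormal before dosing. Its lead-in speaks of adverse drug events, which argues against applying it that way, so no loss of dose should be claimed.

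It is also fair to say that a PT/PTT criterion at entry does not address a value that changes by Week 8. It addresses the man's state on entry. The anticoagulant exclusion is the part that matters at both biopsies.

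**Conclusion.** The point holds as a minor safety gap. The written rules admit a man on a stable anticoagulant whose underlying illness is not judged significant, and they leave unclear whether a normal PT/PTT is required before the first open biopsy. The study agent could add to bleeding risk mainly at the Week 8 biopsy, since the first is the baseline sample. An existing anticoagulant would matter at both.

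The size cannot be expressed as a frequency. The documents do not say how many men with Becker muscular dystrophy take anticoagulants or have a prolonged PT/PTT, and they do not show that any such man would in fact be enrolled. The conclusion rests on two readings: that an anticoagulant does not fall under the antiplatelet wording, and that a hematology profile does not unambiguously include coagulation. If the sponsor intended the second to include PT/PTT, that part of the change only states the intention. The case for acting is that the blood is already drawn and the test is already in the panel.

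**What to change.** - In section 6.1.1, extend the antiplatelet exclusion by adding *or any anticoagulant*, with the same 3-week window. Make the matching change in section 10.7.1. State that a prescribed anticoagulant is not to be stopped in order to qualify, so that the rule does not itself create a risk.
- Add an inclusion criterion: *PT/PTT not above the upper limit of normal at screening, result available before the Day 1 biopsy*.
- Leave the PT/PTT trigger in section 6.3.2 as it is. Limiting it to new prolongation after the first dose could miss a man who was normal at Screening but already prolonged in the pre-dose Day 1 sample.

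The change is to protocol wording only. It adds no visit, blood draw or assay. The downside is an occasional extra screen failure, about 0.1 to 1.1 extra men screened if 1% to 10% were to fail, which is an assumed range.
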